7.1.2.9.3 Second Course (Retreatment) Tumor Imaging

Tumor imaging must be performed within 28 days prior to restarting treatment with pembrolizumab and lenvatinib. Local reading (Investigator assessment with site radiology reading) will be used to determine eligibility.

The first on-study imaging assessment should be performed at 6 weeks (28 days \pm 7 days) after the restart of treatment. Subsequent tumor imaging should be performed every 12 weeks (84 days \pm 7 days) or more frequently, if clinically indicated.

Per RECIST 1.1 (Section 7.1.2.9), if tumor imaging shows initial PD, tumor assessment should be repeated 4 to 12 weeks later in order to confirm PD with the option of continuing treatment while awaiting radiologic confirmation of progression. Participants who obtain confirmatory imaging do not need to undergo scheduled tumor imaging if it is less than 4 weeks later and may wait until the next scheduled imaging time point, if clinically stable.

Imaging should continue to be performed until disease progression, the start of a new anticancer treatment, withdrawal of consent, death, or notification by the Sponsor, whichever occurs first. Disease progression may be confirmed 4 to 12 weeks after the first tumor imaging indicating PD, by the Investigator using RECIST, in clinically stable participants.

7.1.2.9.4 Modified RECIST 1.1 Assessment of CNS Disease

Modified RECIST 1.1 will be used as the primary measure for assessment of intracranial tumor response, date of intracranial disease progression, and as a basis for all protocol guidelines related

to intracranial disease status (eg, discontinuation of study treatment). Up to 5 intracranial, previously untreated target lesion in the brain will be followed for response and progression. Size is considered the tumor's largest diameter. Measurements from multiple lesions are summed to calculate the sum of the diameters (SD). The SD calculated on a baseline scan performed within 28 days of study drug initiation will be used as a reference to determine the objective response of the clinically evaluable lesions. All responses must be confirmed at 12 weeks with an equivalent or better response. Please refer to the original RECIST criteria if further reference is necessary. Please see section 7.1.2.9 for response assessment in patients requiring local therapy while on study.

Measurable disease

Specification of a minimal lesion diameter for measurable lesions reduces the potential for variation in the measurement of smaller lesions due to slice selection and volume averaging. The minimal lesion diameter should be greater than or equal to 2 times the section thickness and a minimum of 5mm. A previously irradiated lesion will not be measured as a target lesion unless it is documented to have progressed since treatment.

Non-measurable disease

Non-measurable lesions at baseline are important in clinical trials because tumor progression may occur at these sites. Non-measurable lesions include enhancing lesions that are less than the specified smallest measurable diameter (5mm when slice thickness is 2.5mm or twice the slice thickness), hemorrhagic or predominantly cystic or necrotic lesions that are difficult to accurately measure and track, and lesions that are indeterminate for metastatic disease. Intrinsic T1- hyperintensity is noted within hemorrhagic lesions that may be misinterpreted as enhancing tumor, and for this reason, the precontrast T1-weighted image must be examined at baseline to prevent this error. Non-measurable lesions should be briefly described on the imaging case report form for each study {Henson, 2008 #303}.

RECIST 1.1 limits the number of lesions measured to 5 in total, with 2 per organ. For our purposes, even if there are multiple measurable lesions in the brain, the sum of diameters of up to a maximum of 5 of the largest lesions will be considered for response assessment.

Modified response criteria for brain metastases

Complete Response (CR): Disappearance of all target lesions.

Partial Response (PR): At least a 30% decrease in the sum of diameters of target lesions, taking as reference the baseline sum diameters.

Progressive Disease (PD): At least a 20% increase in the sum of diameters of target lesions, taking as reference the smallest sum recorded since the treatment started or the appearance of one or more new lesions (new lesions must be greater than slice thickness).

Stable Disease (SD): Neither sufficient shrinkage to qualify for PR nor sufficient increase to qualify for PD, taking as reference the smallest sum diameters since the treatment started. Please refer to RECIST v1.1 for additional details regarding response criteria.

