Archival tissue from extracranial and/or CNS metastases will be obtained, if available, for correlative studies. A baseline pre-treatment fresh biopsy will also be required from an accessible metastasis unless there is not an easily accessible site to biopsy or if a biopsy is determined to be unfeasible by the treating physician after discussion with the study PI. The tumor tissue will be studied retrospectively for PD-L1 expression, TIL characteristics, and other immune and angiogenic markers that may predict sensitivity to this drug combination.

First response assessment will be performed at 6 weeks and will include MRI of the brain and CT body scans (or other clinically indicated body imaging such as MRI or PET CT) to assess systemic disease. Brain metastasis response will be determined using modified RECIST (mRECIST) 1.1 criteria, and extracranial disease response will be determined using RECIST 1.1. Responses will be confirmed with repeat imaging done at 12 weeks. Subsequent imaging will be performed at 12-week intervals thereafter and include an MRI of the brain along with body imaging, which may include CT, MRI, or PET/CT, as clinically indicated. Patients will discontinue treatment for disease progression,

[figure not shown]
unacceptable toxicity, patient withdrawal from the study, termination of study, or death. Patients may be treated beyond progression of intracranial metastases after consultation with the study PI, provided symptomatic lesions are treated with stereotactic radiosurgery (SRS) or surgery. Dose reduction of pembrolizumab for immune-related toxicities is not permitted. Dose-reduction of lenvatinib for related toxicities is permitted.

Number of Patients:

A total of up to 62 eligible patients will be enrolled (27 patients with melanoma with allowance for 3 additional patients if any are unevaluable and 29 patients with RCC with allowance for 3 additional patients if any are unevaluable). Either cohort can be stopped for futility according to Simon's two-stage design. The study will accrue for approximately 36 months and will be open for approximately 24 additional months as patients on study are followed.

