4.2.3 Rationale for Endpoints

4.2.3.1 Efficacy Endpoints

Primary endpoint:

Best brain metastasis response rate (BMRR), defined as PR and CR per modified RECIST 1.1.

Secondary endpoints:

Best overall objective response rate, defined as PR and CR per RECIST 1.1.

PFS, defined as the time from start of study drug administration to the date of the first documentation of disease progression or death from any cause, whichever occurs first.

OS, defined as the time from start of study drug administration to date of death from any cause.

Duration of brain metastasis response, defined as the time from response to the time of the first documentation of intracranial disease progression.

Safety and rate of adverse events, particularly neurologic adverse effects, which include worsening of edema and development of radiation necrosis.

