5.3 Treatment Allocation

This is a phase 2, non-randomized study with 2 cohorts of anti-PD-1/PD-L1 experienced patients with untreated brain metastases: 1) melanoma and 2) RCC. After establishing eligibility, patients will undergo fresh biopsy of a metastatic site, if feasible. The biopsy requirement can be waived

if there is not an easily accessible site to biopsy or if a biopsy is determined to be unfeasible by the treating physician after discussion with the study PI. Archived metastatic tumor tissue, including prior CNS tumor tissue, should also be submitted, if available. The tumor tissue will be studied retrospectively for PD-L1 expression, TIL characteristics, and other immune and angiogenic markers that may predict sensitivity to this drug combination. Pembrolizumab 200mg IV every 3 weeks will be administered in combination with lenvatinib 20 mg PO daily.

MRI of the brain will be obtained after 6 weeks of therapy for initial assessment of efficacy by mRECIST, and a confirmation scan will be performed at 12 weeks. CT body scans (and/or MRI or PET CT as clinically indicated) will also be done at these times to evaluate for extracranial response by RECIST. The next MRI brain or body imaging will be done every 12 weeks thereafter. Patients will continue on study until they have overall disease progression in either their clinically evaluable CNS lesions or in their systemic metastases, toxicities that preclude continuing the study drug, withdrawal from study, termination of study, or death. Dose reductions for immune-related toxicities will not be allowed.

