7.1.2.9.2 Tumor Imaging During the Study

The first on-study imaging assessment for best BMRR by brain MRI should be performed at 6 weeks (42 days ± 7 days) from the date first study dose. Response assessment will be confirmed at 12 weeks. Subsequent tumor imaging should be performed every 12 weeks (84 days ± 7 days) or more frequently if clinically indicated. Imaging timing should follow calendar days and should not be adjusted for delays in cycle starts. Imaging should continue to be performed until disease progression is identified by the Investigator.

Best overall objective response should be confirmed by repeat imaging assessment. Initial best overall response assessment will be done by CT scans (preferred) performed at 6 weeks (42 days \pm 7 days) from the date first study dose. Response assessment will be confirmed at 12 weeks. Subsequent tumor imaging should be performed every 12 weeks (84 days \pm 7 days) or more frequently if clinically indicated. Imaging timing should follow calendar days and should not be adjusted for delays in cycle starts.

Participants who have disease progression may continue on treatment at the discretion of the Investigator and study PI provided they have met the conditions detailed in Sections 5.5.4.

In participants who discontinue study treatment, tumor imaging should be performed at the time of treatment discontinuation (\pm 4 week window). If previous imaging was obtained within 4 weeks prior to the date of discontinuation, then imaging at treatment discontinuation is not mandatory.

In participants who discontinue study treatment without documented disease progression, every effort should be made to continue monitoring their disease status by tumor imaging using the same imaging schedule used while on treatment (every 12 weeks) to monitor disease status until the start of a new anticancer treatment, disease progression, pregnancy, death, withdrawal of consent, or the end of the study, whichever occurs first.

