7.1.2.9.6 Evaluation of Best Overall Response

The Best Overall Response is the best response recorded from the start of the treatment until disease progression/recurrence (taking as reference for progressive disease the smallest measurements recorded since the treatment started). The patient's best response assignment will depend on the achievement of both measurement and confirmation criteria. The best response will take into consideration both the clinically evaluable brain metastases and systemic metastases, and therefore will include measurements from both mRECIST criteria (in the brain) and RECIST criteria (in the body) as follows:

Complete Response (CR): Disappearance of all target lesions in the brain and systemic disease.

Partial Response (PR): Partial response in both the brain and the systemic disease, or if there is PR at one site and SD at the other, the sum of diameters from the brain and systemic disease will be added and the best overall response will be considered PR if there is at least a 30% decrease, taking as reference the baseline sum diameters.

Progressive Disease (PD): Progressive disease in either the brain or the systemic disease will qualify as PD as the best overall response.

Stable Disease (SD): Stable disease in both the brain and systemic disease, or if the sum of diameters from the brain and systemic disease does not qualify for PR or PD (at least a 20% increase in the sum of diameters of target lesions), taking as reference the smallest sum diameters since the treatment started.

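### Read literally, the week-12 confirmation rule leaves an intracranial response first seen at week 12 or later with no way to count, although the primary endpoint is a best response rate with no time limit

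*Combined protocol and SAP*

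**What the plan says.** Four sections of the protocol give the confirmation rule, and all name the same visit.

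- Section 7.1.2.9.4, the response criteria for the brain: "All responses must be confirmed at 12 weeks with an equivalent or better response".
- Section 2.1: "Responses will be confirmed with repeat imaging done at 12 weeks".
- Section 5.3, after the week-6 MRI: "a confirmation scan will be performed at 12 weeks".
- Section 7.1.2.9.2, after setting the first scan at 6 weeks from the first dose: "Response assessment will be confirmed at 12 weeks". It continues: "Subsequent tumor imaging should be performed every 12 weeks".

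The primary endpoint is defined in section 4.2.3.1: "Best brain metastasis response rate (BMRR), defined as PR and CR per modified RECIST 1.1". That definition has no time limit.

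Section 7.1.2.9.6, on the combined brain-and-body response, says: "The Best Overall Response is the best response recorded from the start of the treatment until disease progression/recurrence". Its next sentence adds: "The patient's best response assignment will depend on the achievement of both measurement and confirmation criteria".

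Section 8 (the SAP) does not mention confirmation. Section 8.2 gives the targets as true brain response rates of 20% (melanoma) and 30% (RCC), without saying whether these are best, confirmed or week-12 rates.

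**The concern.** The rule ties confirmation to one calendar visit and not to the date of first response. A week-6 response can be confirmed at week 12. A response first seen on the week-12 scan cannot be confirmed by that same scan, and one first seen at week 24 comes after the only visit named. Taken literally, the endpoint becomes response by week 6 (or on an unscheduled scan before week 12) that persists at week 12. That is not what a best response rate with no time limit describes.

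Single patients decide these cohorts. The melanoma cohort stops at 0 responses in 13 and succeeds at 4 in 27. The RCC cohort stops at 2 or fewer in 18 and succeeds at 7 in 29. One patient with a first response at week 12 could be scored either way by two careful readers, and that patient could settle the result. The trial is open-label and multisite, so the rule should be fixed before the question arises.

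**Working it through.** **1. Which responses can be confirmed.** Scans are timed from the first dose (sections 6.1 and 7.1.2.9.2).

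| Response first documented | Confirmed at week 12? | Next scheduled brain MRI |
|---|---|---|
| Week 6 | Yes | Week 12 |
| Unscheduled scan between weeks 6 and 12 | Yes | Week 12 |
| Week 12 | No, it is the same scan | Week 24 |
| Week 24 | No, week 12 has passed | Week 36 |

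Reading the rule as 12 weeks after first response does not fit: a week-6 response is confirmed at week 12, which is 6 weeks later.

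**2. The plan's own designs.** Inputs are from section 8.2. Let n1 be the stage-1 size, r1 the futility bound, n the total and r the number needed to reject. With response probability p,

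P(reject) = P(X_n ≥ r) − Σ_{x ≤ r1} P(X_n1 = x) · P(X_(n−n1) ≥ r − x), all binomial.

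Melanoma (n1 = 13, r1 = 0, n = 27, r = 4), p = 0.20: 0.8177 − 0.0550 × 0.3018 = 0.801. At the 5% null the result is 0.042.

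RCC (n1 = 18, r1 = 2, n = 29, r = 7), p = 0.30: 0.8120 − (0.0016 × 0.0216 + 0.0126 × 0.0782 + 0.0458 × 0.2103) = 0.8120 − 0.0106 = 0.801. With 12% as the null, the result is 0.0497. Section 8.2 cites 12% as a historical rate but does not label it the null; the power figures do not depend on it.

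Both designs reproduce the stated 80% power with type I error below 0.05.

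**3. Effect of losing late responses.** Let f be the share of responders whose response is first documented at week 12 or later. The documents do not give f, so it is an assumption shown as a range. Suppose the targets mean best response at any time and every late response is lost. The countable rate is then p × (1 − f). At f = 20%:

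- Melanoma, p = 0.20 × 0.8 = 0.16: 0.6471 − 0.1037 × 0.1742 = 0.629.
- RCC, p = 0.30 × 0.8 = 0.24: 0.5644 − (0.0072 × 0.0059 + 0.0407 × 0.0283 + 0.1092 × 0.0992) = 0.5644 − 0.0120 = 0.552.

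| f (assumed) | Power, melanoma | Power, RCC | Stage-1 futility stop, melanoma | Stage-1 futility stop, RCC |
|---|---|---|---|---|
| 0 | 80.1% | 80.1% | 5.5% | 6.0% |
| 10% | 72.4% | 69.1% | 7.6% | 9.9% |
| 20% | 62.9% | 55.2% | 10.4% | 15.7% |
| 30% | 51.8% | 39.9% | 14.1% | 23.8% |

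The last two columns are the chance of stopping a regimen whose any-time response rate equals the target.

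**4. If the targets already mean week-12-confirmed response,** the countable rates are 20% and 30%, and the f = 0 row applies.

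**5. Type I error.** The literal rule can only remove responses from the count, so it cannot raise the chance of rejecting the null.

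**The case against.** The wording can be read as a scan schedule and not as an exclusion. Sections 5.3 and 7.1.2.9.2 put the 12-week confirmation directly after the week-6 scan, as if only describing when the second scan falls. Section 7.1.2.9.7 asks for confirmation by imaging without naming a visit, and section 7.1.2.9.4 sends readers to RECIST for further reference. This stands as evidence that the sponsor may intend to count later responses. It does not supply a rule: section 7.1.2.9.4 covers all responses in explicit terms, and no section says how an intracranial response first seen at week 12 or later is confirmed.

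A reader might take section 7.1.2.9.6 as a promise that any response up to progression counts toward the primary endpoint. It is not. It concerns the combined brain-and-body endpoint, and it makes that endpoint depend on confirmation too. For the primary endpoint the conflict is between section 4.2.3.1 and the week-12 rule.

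A reader might also infer that the trial has lost power because its targets refer to best response. Section 8.2 does not say so, and no section supports any particular share of late responders. Both parts of this objection stand, so the power figures are conditional. The conflict in the definition is not.

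**Conclusion.** The concern holds as a conflict in the primary endpoint definition. Followed literally, the protocol drops a partial or complete response first documented at week 12 or later from an endpoint described as a best response rate with no time limit.

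The size is unknown. Under two assumptions, that the targets mean any-time best response and that 10% to 30% of responders are late, power falls from 80% to between 72% and 52% in melanoma and between 69% and 40% in RCC. If the targets already mean week-12-confirmed response, the stated power stands.

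It would be too strong to say that the sponsor means to exclude late responses, or that the design is underpowered; the documents establish neither. Nor does the rule inflate type I error: it makes the test conservative. The point still needs correcting before any response is counted, because the rule as stated affects both the futility look and the final decision.

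**What to change.** In sections 2.1, 5.3, 7.1.2.9.2 and 7.1.2.9.4, replace the fixed 12-week visit with confirmation on a subsequent brain MRI at least 4 weeks after the response is first documented, at any time before intracranial progression. For a week-6 response that is the week-12 scan; for a later one it is the next scheduled MRI. With the ±7-day windows, the week-6 scan falls no later than day 49 and the week-12 scan no earlier than day 77. The gap is at least 28 days, so the 4-week minimum does not disqualify that pair.

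Refer to this rule in section 8.3, and use the same confirmed-response definition at stage 1 and at the final analysis. In section 8.2, say that the null and target rates refer to this definition. If they were set for week-12-confirmed response, recheck them, because the amended rule can count more responses.

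Add a stage-1 rule, since the amended definition would otherwise leave that count open-ended. A cohort is not stopped for futility while an unconfirmed response that could cross the bound is awaiting its next scheduled MRI. That means any pending response in melanoma when none is confirmed, and in RCC enough pending responses to bring the confirmed count to 3 or more. State a minimum follow-up for the stage-1 patients.

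No extra scans are needed. The cost is time: a response first seen at week 12 is not final until week 24, and one first seen at week 24 not until week 36, so the stage-1 decision may come later. Late responses must also last longer to be confirmed (12 weeks against 6), which follows from the existing schedule.

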7.1.2.9.5 RECIST Assessment of Disease

RECIST 1.1 will be used as the primary measure for assessment of overall systemic tumor response, date of disease progression, and as a basis for all protocol guidelines related to disease status (eg, discontinuation of study treatment).

RECIST 1.1 stipulates that the number of lesions required to assess tumor burden for response determination has been reduced to a maximum of five total lesions (two lesions maximum per organ). Briefly, measurable lesions must have a minimum size of 10 mm by CT scan (CT scan slice thickness no greater than 5 mm) in at least one dimension. Lesions with a longest diameter of <10 mm are considered non-measurable lesions and will be tracked as non-target disease. Tumor lesions in a previously irradiated area, or in an area subject to other loco-regional therapy, are not considered measurable unless there has been demonstrated progression in the lesion. For complete definitions of measurable and non-measurable disease, please refer to the RECIST v1.1 criteria.

7.1.2.9.6 Evaluation of Best Overall Response

The Best Overall Response is the best response recorded from the start of the treatment until disease progression/recurrence (taking as reference for progressive disease the smallest measurements recorded since the treatment started). The patient's best response assignment will depend on the achievement of both measurement and confirmation criteria. The best response will take into consideration both the clinically evaluable brain metastases and systemic metastases, and therefore will include measurements from both mRECIST criteria (in the brain) and RECIST criteria (in the body) as follows:

Complete Response (CR): Disappearance of all target lesions in the brain and systemic disease.

Partial Response (PR): Partial response in both the brain and the systemic disease, or if there is PR at one site and SD at the other, the sum of diameters from the brain and systemic disease will be added and the best overall response will be considered PR if there is at least a 30% decrease, taking as reference the baseline sum diameters.

Progressive Disease (PD): Progressive disease in either the brain or the systemic disease will qualify as PD as the best overall response.

Stable Disease (SD): Stable disease in both the brain and systemic disease, or if the sum of diameters from the brain and systemic disease does not qualify for PR or PD (at least a 20% increase in the sum of diameters of target lesions), taking as reference the smallest sum diameters since the treatment started.

